**ABSTRACT**

Alcohol dependence (AD) is a common problem with significant health consequences. Treatment of AD is evolving to include both counseling methods and medications. Several medications have been discovered, that show efficacy in AD, e.g. naltrexone, acamprosate. However, the overall effect of existing medications is modest leaving a clear need for the development of new pharmacotherapies. The GABAB receptor agonist baclofen has attracted attention as a potential new medication for AD based on preclinical data and early clinical trials. Baclofen is an FDA approved medication with an excellent safety profile even for patients with liver cirrhosis—a not uncommon consequence of AD. Questions have arisen with regards to the efficacy of baclofen and whether higher doses of baclofen are safe and more effective than the prior tested dose of 30 mg/ day. There is emerging evidence that severity of dependence is positively associated with baclofen response. The main goal of the present proposal is to test the efficacy and safety of 30 mg/d and 90 mg/d of baclofen compared to placebo controlling for severity of dependence as assessed by drinks/drinking day. A primary secondary goal will examine for an anxiolytic effect of baclofen.

This study proposes to enroll 120 men and women with AD in a randomized, placebo-controlled trial to include at least 60 individuals with more severe AD ( $\geq 14$  drinks/drinking day for men;  $\geq 10$  drinks/drinking day for women) with randomization to baclofen or placebo balanced for this variable. Baclofen will be titrated to 10 mg t.i.d over 3 days and to 30 mg t.i.d over 12 days and maintained at that level for 12 weeks and then downtitrated for a total study time of 16 weeks. Medical Management will be provided to encourage progress towards drinking goals and to enhance retention and compliance. Drinking patterns, anxiety levels, sleep patterns, craving for alcohol, gamma-glutamyl transferase (GGT) and carbohydrate deficient transferring (CDT) will be assessed. Trough blood levels of R & S-baclofen will be assessed in all individuals at week 4.

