### **Randomization**

A minimization random assignment procedure will be used to match subjects on the key moderator (DDD).(< 14 DDD or  $\geq$ 14 DDD for men and <10 DDD or  $\geq$ 10 DDD for women. This minimization random strategy for assignment to condition was developed specifically for research studies where the number of matching criteria is large for the number of subjects in a study (White et al,1978). In contrast to stratified randomization, which aims for equal numbers of subjects in each treatment for every possible combination of the prognostic variables, the minimization method restricts its aim to equalizing treatment numbers at the different levels of each variable taken separately. Thus, with minimization, there is not the problem that there are more combinations of variables than planned participants. Minimization is particularly superior to stratified randomization when the number of strata is large in comparison with the number of subjects (i.e., not enough subjects to fill every cell). The data analysis team has used this procedure in previous clinical trials and have found no significant differences on the matching criteria in any study (Linehan et al. 2008).

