
For Aim 2, our main interest is the moderation effect of pre-treatment drinking rates on the BAC effect during treatment, for which we have some evidence as indicated in our Figure 1. Power calculations of a significant DDD x treatment interaction were implemented through SAS power procedure PROC GLMPOWER. Power derivations depended on an expected effect size, where based on the Addolorato et al. (2002) finding in a sample consisting of more DDD pre-treatment, we expect a large effect for BAC compared to PBO for those(Cohen's  $d > 1$ ), whereas Garbutt et al. (2010) in a sample consisting of lower DDD pre-treatment, found no difference (Cohen's  $d=0$ ). The pattern of this behavior is consistent with Figure 1 where more separation between BAC and PBO is evident in those with higher pre-treatment DDD. To detect this interactive behavior in our proposed design, where we assume an effect size of 1.2 corresponding to a difference of 28% in %HDD/%ABS rates in the Heavy Drinking group, and an effect size of 0 within the non-Heavy drinking group, the study will have 86.7% power to detect a significant interaction between Heavy drinking and BAC assignment. Accounting for 16.2% attrition provides 80.2% power to detect the same effect. Power calculations for the moderation assume 40 per treatment arm, with pre-treatment heavy drinking balanced per arm (20 low and 20 high).

For Aim 3, power is comparable to Aim 1, where we will have 82.2% power to detect a BAC effect for anxiety or an effect size of 0.5 and 82.0% power to detect an effect size of 0.55 while accounting for 16.2% attrition.

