**Primary Efficacy Analysis:** For the Summary measure, we will fit a general linear model on the outcome variable, consisting of main effect for treatment status. Goodness-of-fit, will be analyzed for outliers and influential observations. While these summary measure approaches are simple to implement and commonly used, information concerning the effect of time on the treatment effect is ignored. To understand the impact of time we will also conduct a repeated measures models analysis. From the weekly usage measures we will fit a mixed effects model consisting of main effect for treatment status. This repeated measures approach provides more information about the effect of treatment over time and therefore, more power compared to summary analyses above. We will also include the interaction of time and treatment. The interaction of time and treatment will answer the question as to whether the treatment effect is consistent over the entire treatment period or varies over the weeks. The mixed effects framework offers flexibility for the outcomes, e.g. any usage versus none, or count outcome data, e.g. number of abstinent days (Wolfinger and O'Connell, 1993). Appropriate covariance structure will be determined based on the AIC (Akaike Information Criteria) and BIC (Bayesian Information Criteria). We will evaluate the baclofen effect for changes in CDT using the mixed model approach described above. Within all framework, statistical contrasts will allow us to compare the two levels of BAC to PBO, as well as statistically contrasting the two levels of BAC. The advantage of the statistical contrasts is it allows us to use all available data to estimate the variance (variance-covariance for the repeated measures) of the outcome, while also properly distributing the degrees of freedom for the analytical test to account for the three levels of treatment.

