**Treatment of Missing Data:** With repeated assessments, missing data/attrition is inevitable, but the key thing is that the specified contrasts are not affected due to the presence/absence of data. We will use pattern-mixture models to assess if there is bias due to drop out or missing data (Hedeker and Gibbons, 1997). To address missing data in the survival models, Dupuy and Mesbah(2004) considered jointly modeling time to event data with missing covariate data in order to assess if the missing data is ignorable or non-ignorable. These approaches will be implemented to the fitted cox model. Days in treatment may directly impact the treatment comparison for assessing differences. To control for this potential issue, we will also assess Marginal Structural Cox Regression models (Xiao et al., 2010).

**Adjustment for Covariates:** All modeling approaches allow for the inclusion of covariates. We will include any measures differing at baseline or important potentially confounding measures (i.e. gender, race) in our models to disentangle the intervention effect from these measures

**Specific Aim 2. To test the hypothesis that a history of heavy drinking as assessed by average drinks/drinking day in the 30 days preceding screening predicts baclofen response in alcohol dependence.**

We will include the pre-treatment HDD measure in all models above to examine its predictive merit, as well as its potential moderating impact of the baclofen effect. Moderation effect will be assessed by including the interaction of pre-treatment HDD with the treatment assignment. We will treat pre-

treatment HDD as a continuous measure. We will use mean profile plots based on quartiles of HDD to assess if the continuous measure has a linear, piecewise linear, or curvilinear effect. .

**Specific Aim 3. To test the hypothesis that baclofen, 30 mg/d and 90 mg/d, is superior to placebo in reducing anxiety in alcohol dependence.**

Our analytic procedure is as described in Aim 1 using mixed effects model to account for the repeated measures over time, while contrasting the mean intervention effect as well as assessing the potential moderation effect of pre-treatment HDD.

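### The plan does not fix whether, or in what form, baseline drinking enters the primary Aim 1 test, and its imbalance rule will almost never admit the allocation factor

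*Combined protocol and SAP*

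**What the plan says.** Four parts of the Combined protocol and SAP bear on the Aim 1 model.

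- **Section 7.2, Primary Efficacy Analysis.** For the summary measure, "we will fit a general linear model on the outcome variable, consisting of main effect for treatment status". The weekly mixed model has treatment, with time by treatment added later. Neither names a baseline term.
- **Section 7.2, Adjustment for Covariates.** "We will include any measures differing at baseline or important potentially confounding measures (i.e. gender, race) in our models". This rule has two limbs, imbalance or confounding. It gives no criterion for imbalance and names only gender and race.
- **Section 7.2, Specific Aim 2.** "We will include the pre-treatment HDD measure in all models above to examine its predictive merit". The measure is continuous, and its interaction with treatment tests moderation. The aim itself, and the power text in Section 7.1 ("Power calculations of a significant DDD x treatment interaction"), are about DDD and not HDD.
- **Allocation.** Sections 5.3, 5.4, 5.6 and 6 (Randomization) balance the arms on DDD split at 14 for men and 10 for women. Section 5.6 alone adds gender. The Abstract describes the comparison as "controlling for severity of dependence as assessed by drinks/drinking day"; Section 1.5 says the control is achieved by making DDD a randomization variable. Section 6 reports that in earlier trials the data analysis team, using this procedure, "have found no significant differences on the matching criteria in any study".

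The high/low DDD factor is named in no model in Section 7.2.

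**The concern.** Read together, these passages allow at least three Aim 1 models: treatment only, treatment plus continuous DDD, and treatment plus baseline heavy drinking days. A fourth follows if the Aim 2 interaction is also present; the treatment main effect then depends on how the moderator is centred, which the plan does not state.

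The imbalance limb does not settle the matter. It selects covariates on chance differences and not on prognosis, and it leaves the model unknown until the baseline data have been seen. It also works against a factor balanced by design, because such a factor has little or no chance of differing.

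The stakes are precision and prespecification. Baseline drinking is likely to be prognostic and is already collected. If it stays out of the test, that information is lost. A test that ignores a prognostic balancing factor also rejects less often than its nominal level.

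**Working it through.** **Inputs from the plan (Section 7.1).** 120 participants, 40 per arm; pooled effect d = 0.5 (the mean of 0.2 and 0.8); 30 mg versus 90 mg d = 0.6; 20 low and 20 high DDD per arm (Aim 2 power text). **Assumed, because the documents give no correlations:** r between baseline and outcome 0.3, 0.5, 0.7; a between DDD and outcome 0.3 or 0.45; c between DDD and baseline 0.3 or 0.6. No attrition unless stated.

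**1. The plan's own figures.** The pooled contrast is 40 against 80, so SE = sqrt(1/40 + 1/80) = 0.1936 and the noncentrality is 0.5/0.1936 = 2.58 on 117 df. Power is 82.2% at one-sided 0.05, which is the stated figure, and 72.6% at two-sided 0.05. For 30 mg versus 90 mg it is 84.7% one-sided, again as stated, and 75.8% two-sided. The plan does not state sidedness. No covariate is needed to reproduce these figures.

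**2. Baseline outcome against a treatment-only model.** Replace d by d/sqrt(1 − r²) and use 115 df, which pays for the baseline value and the allocation factor but credits only the baseline value.

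| r | pooled, one-sided | pooled, two-sided |
|---|---|---|
| treatment only | 82.2% | 72.6% |
| 0.3 | 85.2% | 76.5% |
| 0.5 | 90.6% | 84.0% |
| 0.7 | 97.4% | 94.8% |

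With attrition (33 per arm, d = 0.55, baseline value only) the two-sided pattern is the same: 72.4% rises to 76.3%, 83.9% and 94.7%.

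**3. If HDD means DDD and continuous DDD is already in.** The starting R² is a² (116 df). Adding the baseline outcome gives R² = (a² + r² − 2arc)/(1 − c²) on 115 df. Example: a = 0.3, r = 0.5, c = 0.3 gives (0.09 + 0.25 − 0.09)/0.91 = 0.275. Two-sided power:

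| a | DDD only | r = 0.3 | r = 0.5 | r = 0.7 |
|---|---|---|---|---|
| 0.3 | 76.6% | 77.6–78.8% | 84.0–85.2% | 95.1–95.6% |
| 0.45 | 81.8% | 81.8–83.2% | 85.7–88.7% | 94.8–96.9% |

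The gain is about 0–2, 4–9 and 13–19 points.

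**4. If HDD means baseline heavy drinking days.** For %HDD the plan then already has the outcome's own baseline: 76.6%, 84.1% and 94.8% on 116 df. With the allocation factor added, simulation gives 75.7–77.4%, 83.6–84.4% and 94.9–95.3%. The gain is about nil, so any gain is mainly for %ABS.

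**5. The allocation factor alone.** Simulated two-sided power (20,000 trials) goes from about 73% to 75% at a = 0.3 and from about 74% to 78% at a = 0.45 when the factor joins a treatment-only model. At a = 0.3 it adds nothing if continuous DDD is already in.

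**6. Level of the unadjusted test.** With the factor balanced exactly and explaining a share R² of outcome variance, a normal approximation to the two-sided rejection rate is 2(1 − Φ(1.96/sqrt(1 − R²))). For R² = 9%, 15% and 20% this gives 4.0%, 3.4% and 2.8%. Simulation (40,000 null trials) gives 4.0%, 3.3% and 2.8%, against 4.8–4.9% with the factor in the model. If continuous DDD explains those shares, the unadjusted rates are 4.4%, 3.9% and 3.5%.

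**7. The imbalance limb.** Read differing as a three-arm ANOVA p < 0.05 (assumed). A factor split 20/20 in every arm cannot differ. Continuous DDD qualifies in 0.01% of simulated trials (normal DDD) to 0.09% (lognormal). An unmatched measure qualifies in about 5%, and a baseline measure correlated 0.3, 0.5 or 0.7 with DDD in 4.0%, 2.8% or 1.5%.

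**The case against.** The strongest reply is that the Aim 2 text already supplies the missing term. Taken plainly, it puts a baseline drinking main effect into the Aim 1 models and adds the interaction as a separate step. A reader who stops at the Primary Efficacy Analysis might infer that baseline drinking is left out altogether. The documents do not support that. What stands is narrower: the sentence sits under Aim 2, uses a label that does not match its own aim, and does not say which fit carries the primary test.

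The other points, and what remains of each:

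- The confounder limb could admit baseline drinking by judgement. This is true, and step 7 covers the imbalance limb only. But that limb is open-ended and names only gender and race.
- The Abstract's wording need not mean model adjustment, since Section 1.5 places the control in randomization. This also stands, so the Abstract alone does not prove a contradiction. Balancing on a factor is still a reason to put it in the model.
- The large gains belong to the baseline outcome at r of 0.5 to 0.7, not to the DDD factor. This is correct, and the factor's own contribution is small.
- Section 7.1 bases Aim 1 power on summary scores, which points to the summary model as the leading one. That is a fair inference, but it does not settle that model's covariates.

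**Conclusion.** The point holds as a defect of efficiency and prespecification. The plan allows several Aim 1 models, does not say which gives the primary test, confuses HDD with DDD, and never names its allocation factor in a model. The imbalance limb admits continuous DDD in under 0.1% of trials, if differing means p < 0.05.

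A reader might infer bias, an inflated false-positive rate or a wrong power figure. None follows. The unadjusted estimate is unbiased, its test is valid and errs on the conservative side, and 82.2% reproduces without any covariate.

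The size depends on which model is meant and on correlations that the documents do not give. Two-sided power could gain about 4, 11 or 22 points over a treatment-only model (72.6% to 76.5%, 84.0% or 94.8%) at r = 0.3, 0.5 or 0.7. It gains 0–2, 4–9 or 13–19 points if continuous DDD is already in, and about nothing for %HDD if its own baseline is already in. The allocation factor alone is worth about 2–4 points. The simulations assume normal outcomes and exact 20/20 balance, which minimization only approximates.

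**What to change.** In Section 7.2:

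- Define the Aim 1 model as treatment (three levels), the pre-treatment Timeline Followback value of the same outcome (same scale, window stated) and the high/low DDD allocation factor. Add gender if Section 5.6 is confirmed against Sections 5.3, 5.4 and 6 as describing the allocation.
- Read the primary treatment test from this model without the moderator interaction, which stays in Aim 2.
- Use the same covariates in the weekly mixed model, and baseline STAI-State for Aim 3.
- Replace the imbalance rule with a closed, named list of covariates.
- Reconcile HDD with DDD under Aims 2 and 3.
- Keep the unadjusted model as a sensitivity analysis.

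This is a free improvement. The Timeline Followback and STAI-State are collected before treatment and the DDD category is known at allocation. The cost is two or three of 117 degrees of freedom.

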## 7 Statistical Plan

### 7.1 Sample Size Determination

Aim 1. Our power calculations are based on the summary scores over the 12 weeks of treatment (%HDD and %ABST). Under our modified design, we must consider our 3 group design. We use Cohen's (1988) effect size definition for standardized difference for our continuous outcomes, coupled with the work of Addolorato et al. (2011) as guidelines for our power estimates and anticipated effect sizes. The Addolorato et al. (2011), similar to our design consists of 2 medication groups and a PBO reference reports contrast of incidence rates between the medication arms and PBO. Thresholds of the size of the contrasts, for comparability to the Cohen guidelines, are as defined by Rosenthal (1996) who parallels Cohen's (1988) terminology of small, medium, and larger effects for qualitative indexes such as Odds ratios and Incidence rates. Addolorato et al. (2011) saw a small to medium effect size for the contrast between PBO and 30mg. Similarly they saw a medium to large effect for the contrast between PBO and 60mg. Replicating a small effect size(Cohen's  $d=0.2$  for our outcomes) for the contrast between PBO and 30mg coupled with a large effect size (Cohen's  $d=0.8$  for our outcomes) for the contrast between PBO and 90mg, provides 82.2% power with 120 participants (40/arm) in testing the overall baclofen effect as well as 84.7% power to contrast 30 mg to 90 mg under the assumed effect sizes. We assume seeing a large effect size for the PBO-90mg is reasonable due to the medium-large effect seen by Addolorato et al. (2011) 60mg-PBO contrast. Interpreting the effect size for our outcomes, the PBO-overall medication contrast corresponds to a difference of 12% in %HD/%ABS rate between PBO and pooled medication sample over the 12 week period under an arc-sine transformation of the observed individual rates. The effect sizes for the contrast between medication arms corresponds to a difference of 19% in %HD/%ABS rates. We experienced 16.2% attrition in Garbutt et al (2010); therefore, a slightly larger effect size would be required to provide sufficient power for the overall BAC effect. Assuming an average effect size of 0.55, corresponds to a difference of 13% in %HDD/%ABS rate between BAC and PBO, we will have power of 82.0% to detect a statistically significant baclofen effect while accounting for attrition and 78.1% power to detect a significant difference between medication levels at the 0.6 effect size accounting for attrition.

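### The weekly mixed model takes its covariance from AIC/BIC with no robust or small-sample standard error; with simple candidates its type I error can reach about 7–12%, and its claimed power advantage is unsupported for the average effect

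*Combined protocol and SAP*

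**What the plan says.** Section 7.2, Primary Efficacy Analysis, places two analyses under one heading. The first is a general linear model on one summary value per participant. The second is a mixed model on weekly values, with a treatment main effect and also a treatment-by-time interaction. The text credits the second with more information over time and "therefore, more power compared to summary analyses above". Its covariance rule is: "Appropriate covariance structure will be determined based on the AIC (Akaike Information Criteria) and BIC (Bayesian Information Criteria".

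The section does not give a candidate list, a rule for when AIC and BIC disagree, a robust standard error, or a degrees-of-freedom method that allows for estimating the covariance. Its remark on degrees of freedom concerns the three treatment levels. It does not say which of the two Aim 1 analyses decides if they differ.

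Section 7.1 powers the summary analysis only: "Our power calculations are based on the summary scores over the 12 weeks of treatment (%HDD and %ABST". Aim 3 in Section 7.2 uses the mixed model alone. CDT is also assigned to the mixed model, but the Schedule of Assessments collects it only at screening and week 16.

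**The concern.** A treatment contrast averaged over weeks depends on the variance of each participant's mean over those weeks, and so on correlation between distant weeks as well as neighbouring ones. AIC and BIC reward overall fit, which neighbouring weeks can dominate. AR(1) can therefore win on short-lag fit while forcing long-lag correlation towards zero. The variance of a person's mean is then understated and the p-value is too small. Nothing in the plan guards against this.

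For Aim 1, a positive mixed-model result beside a null summary result could be an artefact, yet the text presents the mixed model as the more powerful analysis. For Aim 3 there is no summary test to fall back on.

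**Working it through.** **1. Reproduce the stated power.** Section 7.1: "provides 82.2% power with 120 participants (40/arm) in testing the overall baclofen effect". The effect size of 0.5 is the mean of 0.2 and 0.8, and it is confirmed under Aim 3: "82.2% power to detect a BAC effect for anxiety or an effect size of 0.5". The noncentrality is 0.5 × √(80 × 40/120) = 2.582 with 117 df. A one-sided 0.05 t-test gives 82.2%, matching the plan; a two-sided test gives 72.6%. One-sided testing also reproduces the 84.7% for 30 mg against 90 mg, and, at 33 per arm, 82.0% and 78.1% ("78.1% power to detect a significant difference between medication levels at the 0.6 effect size accounting for attrition"). Sidedness is stated nowhere and should be. The error rates and powers below are two-sided at 0.05.

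**2. Why AR(1) understates the variance.** Assume 12 weekly values with unit variance and correlation at lag k of ρ(k) = w + (1−w)r^k, where w is the stable share and r the weekly decay. The variance of a person's mean is [12 + 2Σ(12−k)ρ(k)]/144, summed over k = 1 to 11. In expectation, an AR(1) fit reproduces the lag-1 correlation, so it implies ρ(k) = ρ(1)^k.

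Take w = 0.5 and r = 0.5:
- Truth: the sum is 38.0, so the variance is (12 + 76.0)/144 = 0.611.
- AR(1) with ρ(1) = 0.75: the sum is 24.38, so the variance is (12 + 48.76)/144 = 0.422.
- Standard error ratio: √(0.422/0.611) = 0.831.
- The critical value 1.980 acts as 1.980 × 0.831 = 1.646, which has a two-sided tail of about 10%.

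The same arithmetic at other settings:

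| w, r | true variance | AR(1) variance | type I error if AR(1) is used |
|---|---|---|---|
| 0.3, 0.3 | 0.402 | 0.227 | 13.9% |
| 0.3, 0.5 | 0.456 | 0.320 | 10.0% |
| 0.2, 0.5 | 0.378 | 0.281 | 9.0% |
| 0.4, 0.7 | 0.619 | 0.524 | 7.1% |

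At all five settings AR(1) beats compound symmetry, by 22 to 553 units of expected −2 log-likelihood at N = 120.

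**3. Simulation with selection.** No treatment effect, 120 participants, 12 weeks, complete normal data, pooled baclofen against placebo, 3,000 trials per scenario, model-based standard errors. The truth in the first four rows is a random intercept (share 0.3–0.5) plus AR(1) (0.5–0.7); the AIC row may also include the AR(1)-plus-noise truth described below.

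| Candidates | week-averaged contrast | treatment main effect |
|---|---|---|
| CS, AR(1) | 6.9–10.4% | 8.7–12.4% |
| plus unstructured, BIC | unchanged | unchanged |
| plus unstructured, AIC | 5.3–8.3% | 7.6–10.0% |
| plus random intercept + AR(1) | about 5% | about 5% |
| Summary-measure test | 4.9–5.3% | not applicable |

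With only CS and AR(1) competing, a truth of AR(1) 0.9 plus noise gave 12.1–12.7%. Adding Toeplitz to the candidates reduced the rate to 5.0–6.4% by AIC and 5.2–9.6% by BIC. When the truth was exactly CS or AR(1), the rate was 4.9–5.1%. When it was a random slope, or AR(1) 0.95 plus noise, the rate was 4.9–6.2% for every candidate set.

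**4. Aim 3.** State anxiety is measured at weeks 1, 2, 3, 4, 6, 8, 10 and 12, then 14 and 16. With AR(1) by visit number over the visits to week 12, the rate is 6.9–12.2% if AR(1) is selected. AR(1) was preferred to CS in four of five settings.

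**5. Power for the average effect** (d = 0.5, covariance known and correct).
- Complete data: summary 72.6%; mixed model with treatment-by-week exactly 72.6%. The equality holds on a common scale because the fitted arm-by-week means are then the raw means.
- Complete data, main-effect model: 72.6% if exchangeable, 72.9–74.3% for mixed structures, 76.3% for pure AR(1) 0.8.
- With 16.2% dropout: summary on available weeks 69.6–71.4%; mixed model 70.6–71.7% (treatment-by-week) or 71.7–74.2% (main effect); completers-only summary 65.0%.

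**The case against.** The strongest reply is that the inflation comes from assumptions outside the documents. The plan lists no candidate set, and no weekly correlations are given. A mixed-effects analysis that also plans pattern-mixture models could naturally include person-level random effects, and then the rate is about 5%. Choosing a covariance by AIC/BIC is an ordinary pre-specified rule. The simulations used normal outcomes, whereas Section 7.2 envisages arc-sine proportions, binary outcomes and counts. All of this stands. A reader might infer that a false-positive rate of 7–12% is a property of the plan; the documents do not support that.

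A reader might also infer that the mixed model can offer no extra power, so that any gain is an understated standard error. That too goes beyond the evidence. With the correct covariance, the main-effect model, which Section 7.2 names first, gains about 0–4 points on complete data. Gains are somewhat larger with dropout, and 6–9 points against a completers-only summary.

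Nor does the concern undermine the first-listed Aim 1 analysis, which held 4.9–5.3% throughout. CDT has two time points, where CS and AR(1) coincide, so the mechanism cannot arise there.

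What remains is that nothing in the plan ensures a well-fitting candidate or protects the standard error if there is none, and Aim 3 has no other analysis.

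**Conclusion.** The concern holds conditionally. If the candidates are CS, AR(1) and unstructured, and weekly outcomes combine a stable level with a decaying part, AR(1) usually wins and type I error for the average contrast is about 7–12%, against about 5% for the summary test. The exception is AIC with unstructured available, where the week-averaged contrast can come down to 5.3%. With a well-fitting candidate the rate is about 5%. The exposed analyses are the second Aim 1 model and Aim 3.

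The power statement is unsupported as a general claim about the average effect: no gain with complete data and treatment-by-week terms, otherwise a modest one. Section 7.1 gives no power figure for the mixed model. This is a cheap improvement worth making, not a fault that invalidates the trial's main test.

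**What to change.** - Name the summary-measure test, or the equivalent week-averaged contrast, as confirmatory for Aim 1.
- For every mixed-model treatment contrast, including Aim 3, use sandwich standard errors with a small-sample correction, whichever structure is selected. In simulation with the BIC-selected model this brought type I error back to 3.5–5.5%.
- Alternatively, pre-specify unstructured covariance with Kenward-Roger degrees of freedom, and name the sandwich approach as the fallback for non-convergence. A fallback is needed because 12 weeks imply 12 × 13/2 = 78 covariance parameters from 120 participants. The correction is needed too: uncorrected unstructured covariance gave 7.3–7.8% in the main-effect model. Kenward-Roger itself was not simulated.
- Limit the power sentence to time-course questions and the use of partial data.

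The cost is one option in the model code and a few sentences, with no change to design, data or sample size. The downside is slightly wider intervals when the selected structure would have been too narrow.
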